3.7 Derived and Study Variables

Table 3 includes all variables that will be collected, the type of variable and the file that will be included, whereas in Table 3 there is a description of the frequency and timing of relevant variable observations and assessments.

Table 3. List of all variables collected through the study

File	Description	Variables	Type
Quest A	Baseline Characteristics	BMI	Continuous
		Age	Continuous
		Education	Categorical (4 Levels)
		Work	Continuous
		Working Experience	Continuous
		Smoking	Categorical (3 Levels)
		Cigarettes/day	Continuous
		Years smoking	Continuous
		Age ex-Smoker	Continuous
		Alcohol	Categorical (4 Levels)
		Alcohol Units	Continuous
		Exercise	Categorical (2 Levels)
		Exercise Hours	Continuous
		A/C Rural	Categorical (4 Levels)
		A/C Urban	Categorical (4 Levels)
		Travel	Categorical (2 Levels)

TEMP Study

		Airplane Frequency	Categorical (3 Levels)
		Screen Hours	Continuous
		Health	Categorical
Chronotype Quest	Sleep/Wake Cycles		
Diary	Meal Intakes	Time / Meal Time / Drink Time	Continuous
		Diary / Meal Description / Drink Description	Categorical
Urine Analysis	Outcome	Adipokines (leptin, adiponectin, ghrelin)	Continuous
	Exposures	Cortisol Melatonin Metabolites (metabolomics)	Continuous
Temperature Analysis	Exposures	Skin temperature Ambient air temperature	Categorical/continuous

3.8 Baseline characteristics

The baseline characteristics (recorded through questionnaire A (Table 3)) will be summarized overall and by study group. Continuous variables will be checked for normality with QQ plots and histograms. Categorical variables will be described with frequencies and percentages, normally-distributed continuous variables with means and standard deviations, and non-normal continuous variables with medians and interquartile ranges (25th-75th percentiles).

Baseline data will be tested for difference between both study groups by

- Chi-squared test for categorical variables

TEMP Study

- T-test for normally distributed continuous variables
- Wilcoxon test for non-normally distributed continuous variables

3.9 Primary analysis of outcomes

3.9.1 Cosinor method

An exploratory analysis will be formed by plotting the data as a function of time for each sampling day. This will allow for visual observation of possible trends and for comparisons between sampling days. Residuals will also be plotted as a function of time that will provide valuable information on how to proceed for further analysis. A histogram will also be used to assess normality of the results.

Since prior information suggests a presence of rhythm with period of 24-hours, data will be stacked in classes in an attempt to reduce noise and reveal the rhythm's waveform. Class means will be used to test for a statistically significant time effect.

Once a rhythm has been validated, the single cosinor method will be used to model the rhythm by fitting a cosine curve, a procedure similar to the least square methods (Cornelissen, 2014). For each subject, a single-component cosinor will be created for each sampling day, and for each group, a population-mean cosinor will be created for each sampling day. These methods also involve certain assumptions that need to be satisfied hence; regression diagnostics will be implemented at this stage to assess the model's adequacy. Further statistical testing will be implemented to test the equality of parameters such as the MESORs, amplitudes and acrophases (Cornelissen, 2014) of the two groups in the two settings.

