2.2 Study Objectives

Primary Objectives:

1. To investigate the effect of skin temperature gradient on the diurnal variation of adipokines and stress hormones in the two settings (urban and rural). (Null hypothesis: There is no association of skin temperature gradient with adipokine secretion.)
2. To investigate the circadian patterns of adipokines (leptin, adiponectin, and ghrelin hormones), cortisol, and melatonin in healthy individuals residing in two different climatological environments: urban and higher in latitude rural. (Null hypothesis: There is no difference in the circadian rhythm of the metabolic hormones between participants at the urban or rural environments.)

Secondary Objective:

1. To examine metabolite differences in the metabolomics-based profiles of healthy individuals with non-obese body weight in two study settings with distinctly different climatological characteristics.

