3.9.3 Primary Analysis

TEMP Study

Linear mixed effect models of the adipokines, cortisol and melatonin levels will be used as a function of the treatment (rural vs urban), accounting for both between and within subject variability by having random intercepts for the participants with unstructured covariance matrix. Non-linear mixed effects models of the adipokines, cortisol and melatonin levels, accounting for their diurnal variation as a function of the treatment, will be also constructed.

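### The cosinor comparison depends on a rhythm test whose level and failure rule are not fixed; applied per setting, it can bar the comparison where one setting flattens a rhythm

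*SAP*

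**What the plan says.** Primary objective 2 (SAP section 2.2) has the null hypothesis "There is no difference in the circadian rhythm of the metabolic hormones between participants at the urban or rural environments". Section 3.9.1 addresses it in sequence. After plotting, "data will be stacked in classes in an attempt to reduce noise and reveal the rhythm's waveform". Then "Class means will be used to test for a statistically significant time effect". Only after that step does the cosinor enter: "Once a rhythm has been validated, the single cosinor method will be used to model the rhythm by fitting a cosine curve". Cosinors are fitted per subject and, as population means, per group, in each case by day of sampling. Last come the tests that answer the objective, which "test the equality of parameters such as the MESORs, amplitudes and acrophases" between groups and settings.

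The section does not state the classes, the test, whether person differences are removed first, or whether the test is run per hormone, per setting, per subject or on both settings together. It gives no rule for a series that fails.

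Section 3.9.3 separately plans linear mixed models of all five hormones by setting. It adds non-linear mixed models "accounting for their diurnal variation as a function of the treatment, will be also constructed". Neither depends on a rhythm test.

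**The concern.** A preliminary test on the outcome decides whether the comparison of that outcome is made. A rhythm present in one setting and flat in the other contradicts the null hypothesis of objective 2. The same flatness makes a series fail a rhythm test. If each setting must pass, the condition withholds the cosinor comparison in a situation where there is a real difference to find.

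Because the level of the test and the consequence of failure are open, both could also be settled after the data are seen. At stake is the only place in the plan where amplitude and acrophase are named as quantities to compare between settings.

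**Working it through.** **The plan's own figure.** The SAP gives no figure for this rule. Its sample size (section 2.9) does reproduce, so 57 is a fair size for illustration: n = 2 × [3.53 × (1.960 + 0.842) / 1.9]² = 54.2, hence 55 by the normal approximation. The exact t calculation gives 57 (power 0.806). This does not bear on the point otherwise.

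**Model.** For each series, y = M + β cos(2πt/24) + γ sin(2πt/24) + error, with amplitude A = √(β² + γ²). The setting comparison tests Δβ = Δγ = 0 on 2 degrees of freedom.

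**A bound that needs few assumptions.** If the rhythm is absent in one setting, a 5% test there passes about 5% of the time. If both settings must pass, power for the comparison cannot exceed about 0.05, however strong the other rhythm.

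**Illustration 1.** From the SAP: 57 subjects, a 5% level, and about 5 samples per sampling day (at least 4 voids plus the next first morning void, section 2.5). Assumed: clock times, acrophase, residual SD 1, and amplitude 0.5 or 1.0 SD in one setting with a stated share kept in the other. Person means are removed before the rhythm test, which is an F test over time classes. The comparison is a paired Hotelling test on subject-level coefficients, F = (N−2)/[2(N−1)] × T². With 600 simulated trials, the simulation standard error is at most √(0.25/600) = 0.02.

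| Amplitude (SD) | Share kept in other setting | No condition | Both settings must pass | Pooled test must pass |
|---|---|---|---|---|
| 0.5 | 0% | 0.88 | 0.04 | 0.75 |
| 0.5 | 25% | 0.69 | 0.06 | 0.67 |
| 0.5 | 50% | 0.33 | 0.09 | 0.33 |
| 1.0 | 0% | 1.00 | 0.05 | 1.00 |
| 1.0 | 25% | 1.00 | 0.50 | 1.00 |
| 1.0 | 50% | 0.89 | 0.88 | 0.89 |

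With amplitude 0.5 and no rhythm in the other setting, the two settings passed in 0.99 and 0.05 of trials, so both passed in 0.99 × 0.05 ≈ 0.05. With identical rhythms, the unconditional comparison rejected in 0.04 to 0.05 of trials, so leaving out the condition does not inflate false positives.

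**Illustration 2.** Assumed: 55 subjects, 5 voids per setting, between-person SD 0.8 and void SD 0.5 (log units), 4-hour classes. Raw values are stacked unless stated.

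| Amplitudes | No condition | Both must pass | Both must pass, person means removed | Pooled test must pass |
|---|---|---|---|---|
| 0.4 vs 0.1 | 1.00 | 0.00 | 0.60 | 1.00 |
| 0.4 vs 0.2 | 0.91 | 0.34 | 0.90 | 0.91 |
| 0.3 vs 0 | 1.00 | 0.00 | about 0.10 | 0.46 |

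- Removing person means raises the pooled figure for 0.3 vs 0 from 0.46 to about 0.99. Between-person variation in the error term therefore accounts for most of that loss.
- If a rhythm in either setting is enough to proceed, power is 0.998, 0.91 and 0.96 in the three rows.
- With amplitude 0.3 in each setting and opposite phases, the two curves cancel when pooled. Power is 1.00 without the condition, 0.89 if both must pass, and 0.00 to 0.01 with the pooled test.
- Sensitivity to the simulation set-up: for 0.4 vs 0.2, separate simulations with the same SDs gave 0.65 to 0.91 without the condition and 0.03 to 0.34 with a raw-value test required in both settings. The exact size is soft; the direction is not.

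**The case against.** The strongest reply is that the damaging reading is not written down. Validating a rhythm may mean one check per hormone on all data, and the section itself starts from prior evidence of a 24-hour period. On that reading the intact setting usually carries the test and little is lost. This stands, with two exceptions: a weak rhythm abolished in one setting when raw values are stacked, and opposed phases. The per-setting reading is also natural, since the plots before the test and the cosinors after it are both organised by sampling day, and each sampling day lies in one setting.

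The second reply is section 3.9.3, which analyses all five hormones by setting whatever the rhythm test shows. This stands too and limits the consequence. It is not a full substitute: the linear model addresses mean level, and the non-linear model has no stated functional form and no MESOR, amplitude or acrophase contrast.

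A reader might infer more than the document supports:

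- That a hormone failing the test is dropped. The SAP states no exclusion; it is silent on failure.
- That the primary circadian comparison is steered to a null result. That ignores section 3.9.3, and a comparison not made is not a null result.
- That flattening is the effect the trial seeks. Objective 2 concerns any difference in rhythm, and shifts in level or phase with both rhythms intact are equally covered.
- That amplitudes among hormones passing the test are biased upward. No calculation here shows this.

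**Conclusion.** The concern holds in a limited form. The cosinor comparison is conditional on a significance test of the same outcome, with neither the level of that test nor the consequence of failure fixed. If both settings must pass, power to detect a rhythm abolished in one setting falls from 0.88–1.00 to between 0 and about 0.10 across the simulations. For partial damping the loss ranges from almost none to nearly all, depending on the size of the rhythm and on whether person means are removed. A pooled test is usually harmless but not always.

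These figures rest on assumed amplitudes, variances, clock times and classes, none of which the SAP gives. The only nearly assumption-free result is the ceiling of about 5% when one rhythm is absent and both settings must pass. The effect is confined to the cosinor comparison. It should be corrected before analysis because the condition protects nothing that the comparison needs.

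**What to change.** Remove the condition from section 3.9.1 and state that:

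1. the cosinor is fitted for all five hormones in both settings, whatever the rhythm test shows;
2. the setting difference is tested for each hormone jointly on the cosine and sine terms (setting × (cos, sin), 2 degrees of freedom), with MESOR, amplitude and acrophase differences reported alongside;
3. the zero-amplitude test is reported per setting as description only;
4. class means are used for plots only.

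The cost is SAP wording; no new data are needed. The drawback is that acrophase is poorly determined where amplitude is near zero. The text should say that such estimates will be flagged as imprecise and shown with their intervals.

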3.9.2 Exposure: Temperature gradient

We define ambient temperature gradient as any change in ambient air temperature of $\pm 2^{\circ}\text{C}$.

We define skin temperature gradient as a minimum change of $\pm 0.1^{\circ}\text{C}$ in skin temperatures. We will examine how exposures in temperature gradient affect the outcome in 3 different ways:

- Frequency: The number of temperature gradient changes within a day.
- Magnitude: The increase/decrease in temperature exposure metric from its previous in time background value of the gradients.
- Duration: The time each temperature gradient lasts.

3.9.3 Primary Analysis

TEMP Study

Linear mixed effect models of the adipokines, cortisol and melatonin levels will be used as a function of the treatment (rural vs urban), accounting for both between and within subject variability by having random intercepts for the participants with unstructured covariance matrix. Non-linear mixed effects models of the adipokines, cortisol and melatonin levels, accounting for their diurnal variation as a function of the treatment, will be also constructed.

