2.1 General aspects

A 2 x 2 cross-over pilot study of healthy adults is proposed to prospectively describe the effect of ambient temperature gradient on diurnal hormonal secretion patterns. A total of 50-60 subjects will be followed for a period of 7 days firstly in an urban environment or in a village of the mountainous rural environment of Troodos and later, for the same period, in the alternate setting, during the summer period in Cyprus. The two settings will allow for the comparison of the circadian patterns of hormones secreted by the adipose tissue among different gradient temperature changes. Continuous quantification of skin temperatures on one day in each setting will allow for characterization of how skin temperature is affected by ambient temperature. Collection of all urine voids on one day in each setting will allow for quantification of the hormone secretion by the adipose tissue. In Table 1 the study characteristics of the non-pharmacological intervention are presented and in Figure 1 the order and duration of various procedures of the study are displayed.

Table 1. Study characteristics

Study Design	Randomised cross-over trial
Study groups	
Two study groups:
 
Group A: People initially staying in their permanent house in the urban area and then moving to the rural area for at least 7 days (Troodos Mountains – holiday house).
 
Group B: People initially staying in the rural mountainous area for at least 7 days (Troodos Mountains – holiday house) and then returning to their permanent house in the urban area.

Blinding	
The blinding of the participants to group assignment is not possible with the present study design. The blinding of the researchers to the subjects' identity is achieved by the coding of all study materials (urine containers, temperature sensors, questionnaires and diaries). The study personnel who will obtain the outcome measurements will be not informed of the group assignment. The personnel who will deliver the

intervention will not take any outcome measurements. All outcome assessors and data analysts will be kept masked to the allocation.

Randomisation Random allocation will be made in blocks in order to keep the sizes of treatment groups similar. Block randomisation with block size=30 and subjects no=60, will be performed using the function RAND() in Excel, that provides a random generated list, by an investigator with no clinical involvement in the trial

[figure not shown]

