2.5 Intervention

Table 2 presents the details of the visits and the sample collection processes.

Table 2. Visits details and sample collection process in chronological order.

Visits/Sampling days	Description
Visit 1	
The researcher visits the participant one day before the sampling day 1 (6 days after being in the urban/rural setting) and the following procedures are performed:
 
 • Administrates the consent form and receives it signed by the participant • Administrates the Questionnaire A and Chronotype Questionnaire and receives them completed by the participant • Provides coded vials for urine sampling in plastic bag and explains • Provides activity diary and explanations • Places temperature sensors on the participant (after activating them on place) and explains • Provides the instructions for urine collection and temperature sensors

	
 • Arranges appointment for the sample collection two days later (ideally in the morning)
Sampling day 1	
The participant is wearing the sensors continuously from the previous day and collects the urine voids of the day (at least 4) except for the first morning void. The participant stores the urine vials in a plastic bag in the freezer/fridge. The participant notes in the activity diary, the activities of the day (including entrance/exit from buildings, sleep/wake cycle, physical activities and meals) and their corresponding time and the times that each urine void was collected.

Visit 2	
The participant collects the first morning void of the day after the sampling day and continues wearing the temperature sensors and noting in the diary.
 
The researcher visits the participant one day after the sampling day on the arranged time and the following procedures are performed:
 
 • Collection of the urine samples and sensors • Collection and check of the completed activity diary • Sensors data are transferred immediately on a laptop, to check that data were recorded • Arrangement for the next visit that will take place in the other setting (urban/rural) with at least 2 days of washout period and on the 6th day in the alternate setting.

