2.9 Sample Size

To estimate the sample size, the sample size program by the MGH Biostatistics Center was used (Schoenfeld, 2010). We used the paired t test study design for calculating the power of this test, assuming that each subject has a pair of values (one for the urban setting and one for the rural mountainous setting). The variable used for the estimation of the sample size was one of the adipokines (serum leptin), since it is one the primary outcomes for the trial and there is no available information for urinary adipokines.

The input parameters were: significance level, within patient standard deviation, power and minimal detectable difference in means. Based on the literature, the within subject standard deviation of plasma leptin was assumed to be 3.53 ppb for females and 0.01 ppb for males (Saad et al., 1998), and we hypothesized a minimal detectable difference in leptin levels between the urban and rural mountainous settings to be atleast 1.9 ppb, based on other intervention studies (Hibi et al., 2017; Fontes-Villalba et al., 2016). Assuming a power of 80% and a two-sided 5% significance level, the sample size for this two-treatment crossover study was estimated to be 57 subjects.

3 Statistical Analysis

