3.2 Populations

Depending on the analysis, different characteristics for inclusion are defined in the population. For example:

In the Full Analysis, population is defined as:

- All subjects who were randomised.
- All subjects who completed both sampling days providing complete follow-up, independent of the duration of the sampling days.
- All subjects who completed both sampling days providing complete follow-up, independent of the stability of sleep/wake cycles and meal intakes.
- All subjects who completed both sampling days providing complete follow-up, independent of the number of received urine vials.

In the Final Analysis, population is defined as:

- All subjects who completed both sampling days providing complete follow-up, except those who dropped out.
- All subjects who adhere to the major criteria in the protocol (e.g. all subjects who stayed healthy or did not travel to another country within the study or completed both sampling days and completed the whole study duration).
- All subjects who did not substantially deviate with regards to sleep/wake cycles and meal intakes
- All subjects except those that have a health problem (diabetes and hypertension) and did not know by the beginning of the study.
- All subjects except those women that were pregnant and did not know by the beginning of the study.

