3.4 Unadjusted and adjusted analyses

The urinary variables will be used with adjustment for creatinine levels to account for urine dilution. If outcomes are not normally-distributed and the analyses require the normality assumption, then outcomes will be log-transformed (natural logarithm).

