3.5 Multiple testing

Multiple testing will be accounted for, using the Benjamini-Hochberg (false discovery rate, FDR) method considering all the regression parameters of the primary and post-hoc analyses. Q-value <0.05 indicates statistical significance of an association after controlling the false discovery rate at 5%.

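### The primary mixed model of this 2x2 crossover has no period term, so unequal sequences turn a common first-to-second shift into an apparent setting effect

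*SAP*

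**What the plan says.** Section 2.1 sets out a randomised 2x2 crossover: Group A stays in the city first and Group B in the mountains first. Section 3.9.3 gives the primary model: "Linear mixed effect models of the adipokines, cortisol and melatonin levels will be used as a function of the treatment (rural vs urban". It adds a random intercept per participant with an unstructured covariance matrix. The companion non-linear models add variation within the day. Neither model names period or sequence.

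No other section supplies the missing term:

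- Section 3.4 adjusts for dilution only: "The urinary variables will be used with adjustment for creatinine levels to account for urine dilution".
- Section 3.9.1 fits cosinors by group and sampling day and compares their parameters. These are separate fits and do not adjust the mixed-model contrast.

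Several statements bear on sequence balance and on the cost of a change:

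- Section 2.1: "A total of 50-60 subjects will be followed for a period of 7 days".
- Section 2.1, Table 1: "Block randomisation with block size=30 and subjects no=60".
- Section 3.2, one condition for the Final Analysis population: "All subjects who did not substantially deviate with regards to sleep/wake cycles and meal intakes".
- Section 2.9: "We used the paired t test study design for calculating the power of this test".
- Section 2.5, Table 2, on each sampling day the participant "collects the urine voids of the day (at least 4) except for the first morning void"; the next first-morning void is collected as well.
- Section 3.5 applies the Benjamini-Hochberg method "considering all the regression parameters of the primary and post-hoc analyses".

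**The concern.** Because the order of the settings is randomised, period can be separated from setting, but only if the model contains it. A random participant intercept cannot do this, since period varies within a person.

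A first-to-second change is plausible. Recruitment runs from July to September, the two sampling days are separated by at least a two-day washout and a further stay to the sixth day, and the study is about outdoor temperature, which may itself drift over that interval.

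The setting contrast is the primary comparison. With unequal sequences, part of any average change between stays would be reported as a setting effect, or would mask one, depending on its direction.

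**Working it through.** **Inputs.** From section 2.9: within-subject SD 3.53 ppb (the value for females), target difference 1.9 ppb, two-sided 5%, power 80%, N=57. From section 2.1: blocks of 30, 60 planned, 50-60 followed. From section 2.5: at least four voids plus the next first-morning void, taken as m=5 per setting. Assumed, because the SAP does not give them: pi of 0.95 and 1.9 ppb; no person-by-day variance; 15:15 within each block.

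**The SAP's own figure.** The variance of the within-person difference is 2 x 3.53^2 = 24.92. The paired t test with difference 1.9 first exceeds 80% power at N=57 (80.6%), so the stated sample size is reproduced.

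**Bias.** Let D = nA - nB. The expected rural-minus-urban difference is effect + pi in Group A and effect - pi in Group B. Without a period term the estimate averages over all N people:

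bias = (nA x pi - nB x pi)/N = pi x D/N

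With a period term the estimate is the unweighted mean of the two sequence means, and pi cancels at any split.

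| Split | D/N | pi = 0.95 | pi = 1.9 |
|---|---|---|---|
| 30:30 | 0 | 0 | 0 |
| 27:23 | 0.08 | 0.08 ppb | 0.15 ppb |
| 30:20 | 0.20 | 0.19 ppb | 0.38 ppb |

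At N=50 the standard error is sqrt(24.92/50) = 0.71 ppb.

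**Variance.** An unmodelled shift adds pi^2(N - D^2/N) to the sum of squares of the differences, SSd.

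- Paired t: the variance is SSd/(N-1). At N=57, 29:28, pi=1.9 the rise is 3.61 x 56.98/56/24.92 = 14.7%.
- Random-intercept model, with SSW the sum of squares between voids within a person and setting: the residual variance is (SSW + (m/2)SSd)/(2N(m-1) + N-1), and SE^2 = 2 x residual variance/(mN). The void variance is 5 x 3.53^2 = 62.30 and the denominator is 512, so the rise is 2.5 x 3.61 x 56.98/512/62.30 = 1.6%.

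Near balance at N=57 (mean of 29:28 and 28:29), power for pi = 0, 0.95 and 1.9 is therefore 80.6%, 79.6% and 76.5% for the paired t, but 81.8%, 81.7% and 81.4% for the random-intercept model. The loss of precision is visible in the sizing test and slight in the planned model.

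**Error rates.** Random-intercept model, N=50, m=5, pi=1.9, 2,000,000 draws per case:

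| Split | Power, setting only (by direction of shift) | Power with period | Type I error, setting only |
|---|---|---|---|
| 27:23 | 82.3% or 69.0% | 76.3% | 5.3% |
| 30:20 | 89.4% or 56.9% | 74.9% | 8.1% |

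With the period term, type I error at 30:20 is 5.0%. Simulating individual voids gave matching results: 8.2% and 7.9% for type I error at 30:20 and 20:30, and 82.7% and 68.7% for power at 27:23 and 23:27.

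**How likely imbalance is.**

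- If recruitment stops at 50, 20 of the 30 places in the second block are used. Hypergeometric(30, 15, 20) gives P(|D| >= 4) = 24.5% and P(|D| = 10) = 0.02%.
- If 10 of 60 are excluded regardless of sequence (an assumed rate), Hypergeometric(60, 30, 10) gives P(|D| >= 4) = 29.9%.

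A 30:20 split would in practice need exclusions concentrated in one sequence.

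**Price of the period term.** The standard error is multiplied by 1/sqrt(1 - (D/N)^2): 1.003 at 27:23 and 1.021 at 30:20. With no shift, power at N=50 goes from 76.6% to 76.3% and from 76.6% to 74.9%. At N=57 it stays at 80.6% (paired t) or 81.8% (five voids).

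**The case against.** The strongest reply is that the bias depends on the split, and that allocation independent of outcome makes it average out. Averaged over the imbalances described above, with pi=1.9, the setting-only model has type I error of about 5.0% if recruitment stops at 50 and 5.1% if 10 of 60 are lost at random, with power of about 75.9% and 75.8%. At N=57 from allocation alone the largest difference is 3, so the bias is at most 1.9 x 3/57 = 0.10 ppb. The most striking figures come from 30:20, which chance hardly produces. These points are right, and they limit the grade. They do not remove the bias in the one split the trial will actually obtain, and exclusions need not be independent of sequence: consent and Questionnaire A come at Visit 1, after six days in the first setting.

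Second, pi has no source, and the ppb scale is serum leptin while the outcomes are creatinine-adjusted urinary values. That stands. The ppb amounts are illustrations, although the fraction D/N applies to any outcome on its analysis scale.

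Third, person-by-day variance could matter more. If it is 20% of day-mean variance, type I error is about 7.5% with or without a period term. That is a separate weakness which this change does not cure.

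Fourth, the cosinors by group and sampling day would make a period shift visible. So they would, but they give no period-adjusted contrast in the mixed model.

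**Conclusion.** The concern holds and should be fixed. The primary linear model of a crossover omits a factor that is known for every sample, and its setting estimate is then off by pi(nA-nB)/N. At a realistic 27:23 split and a shift as large as the target effect, this is 0.15 ppb against a standard error of 0.71 ppb. It moves power by about 6 to 7 points either way and type I error to 5.3%. At 30:20 the effect is serious but the split is unlikely. Near balance it is small, and at 30:30 there is no bias.

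The algebra needs no assumption beyond a shift common to both sequences. The sizes rest on the assumed pi, the serum-leptin scale, five voids per setting and no person-by-day variance.

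**What to change.** In 3.9.3, specify for the linear mixed models: *fixed effects for setting (rural vs urban) and period (first, second)*. Add period to the mean level of the non-linear models. A sequence term is optional. State also that a two-level period term removes only the average first-to-second change; it removes neither all seasonal variation nor differential carry-over.

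In 3.5, add: *Period coefficients are nuisance terms and are not part of the Benjamini-Hochberg family.* This is needed because 3.5 as written would take them in. If the family is the five setting coefficients, five null period coefficients would lower power per hormone from 61.9% to 52.9% when one hormone responds, or from 79.5% to 69.8% when all five do (511 df; with 55 df, 59.2% to 49.5% and 77.7% to 67.0%). If five clearly non-zero intercepts are counted too, the falls are about 5 points (76.0% to 71.0%, and 80.8% to 76.0%). On either reading period is better left out.

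The cost is SAP wording and one degree of freedom, with no new data. Power at N=57 does not visibly change; at N=50 with no shift the loss is about 0.3 points at 27:23 and 1.7 points at 30:20.
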